- Demographic Data: The research assistant (or other member of the research team) will collect routine demographic data from the electronic medical record and/or from the patient's parent or guardian including age in years, gender, race, weight in kilograms, medical comorbidities, procedure type and history of sedation difficulty. Additionally, the parent/guardian will be asked to provide their phone number and select the best time of day for the research assistant (or other member of the research team) to call for phone follow-up, cell phone number to text, provide an email address, and mailing address. Parents will be contacted by the research assistant (or other member of the research team) at 1 week follow up via phone, text, email (via secured REDCap link) and/or mail to complete the post-hospitalization behavior questionnaire (PHBQ) and pain survey. One PHBQ survey and pain survey is completed. This information will be collected by the Research Assistants (or other member of the research team) on questionnaires on REDCap or by paper. See Appendix C.
- Measures:
  - Anxiety: To assess the patient's anxiety, the following assessment tool will be used.
    - Modified-Yale Pediatric Anxiety Score (m-YPAS): See Appendix D.

The m-YPAS is a widely used by medical providers to assess patient anxiety at the time of induction of anesthesia. It is designed to be completed in less than 1 minute. It was originally developed for use in children ages 2-6 years but has since been modified to include adolescents. It is reliable and its validity compares favorably to that of the gold standard, the STAI-C (Kain, Z. 1997). The patient's provider (attending physician or fellow physician) will assess the patient's anxiety using the m-YPAS twice during our study: 1st upon patient arrival and enrollment and 2nd immediately preceding sedation after VR intervention or standard of care (depending on which group patient has been randomized to). This will be given to the research assistant (or other member of the research team) to score. The score will not be shared with the physician.

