- **Procedure Measures:** Variables that might be associated with the primary outcome will be collected. Following the procedure, charts will be reviewed to collect: 1) the type of pain medication given in the ED, 2) the dose (mg/kg and total number of doses) of pain medication given in the ED, 3) the anxiolytic medication given in the ED, 4) the dose (mg/kg and total number of doses) of anxiolytic medication given in the ED, 5) the type of pain medication prescribed for home, and 6) the dose (mg/kg and total number of doses) of pain medication prescribed for home. See Appendices E and F.
- **Outcome Measures:**
  - **Post-Hospitalization Behavior Questionnaire (PHBQ):** See Appendix F. The PHBQ is a parent-report questionnaire with 27 items in six categories, comprising general anxiety, separation anxiety, sleep anxiety, eating disturbance, aggression towards authority, apathy, and withdrawal. This questionnaire has been used extensively since its development in 1966 to study negative behavioral changes in children post-surgery or hospitalization (Kain et al., 1996, Kain et al., 1999) and was recently used to evaluate the same after minor ED procedures (Brodzinski et al., 2013). This questionnaire takes approximately 10 minutes to finish. This tool will be completed by a parent(s)/guardian(s) prior to the sedation and during phone or mail follow-up post-sedation.

Procedures of the study: The study procedure is outlined in the diagram below (Figure 1).

Figure 1. Procedures of the study

Patients will be identified by trained research assistants (or other member of the research team) and enrollment criteria will be reviewed. Parent/guardian consent will be obtained for all eligible patients. A separate assent form will be completed for patient's aged 7- 13 years. Demographic information will be collected from the parent/guardian.

Patient's anxiety measures using the m-YPAS will be completed at baseline by the patient's medical provider (attending physician or fellow physician). A PHBQ will be completed at baseline by the patient's parent. Patients will then be stratified into high and low anxiety groups based on their baseline m-YPAS score (score of 40 or greater being highly anxious) (Pearce, et al., 2017, Kim, et al., 2012, Kain, et al., 2006) and randomized in blocks of 4 by a computer to either the control or experimental group on a 1:1 ratio. See Figure 1.

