The VR headset, device, and software, created by Stanford's Childhood Anxiety Reduction through Innovation and Technology (CHARIOT)program/Weightless Studio, LLC will be utilized in this study. Patients in the VR intervention group will be allowed to select a distraction-based game to play with active VR content featuring interactive avatars and interactive experiences tailored to the pediatric population that allow players to do things such as control penguins sliding down a mountain while collecting pebbles for points, control puppies running in space to collect treats to the rhythm of music, and control an asteroid miner exploring an asteroid belt and collecting points based on color of asteroids collected, for example. See appendix H.

The game will last a minimum of 5 minutes in duration, provided patient tolerance. The patient may play longer if desired prior to receiving procedural sedation and the total length of activity played will be documented by the RA who will record patient's start and stop time. The VR device will not be applied until the pending time of the procedure is known, such that it will be removed from the participant no longer than 5 minutes before the sedation procedure is initiated, provided patient tolerance. The VR device will be removed when the X-ray technician team arrives to the room prior to the start of the sedation. The time from VR removal to the time of m-YPAS assessment and time of sedation medication administration will be collected and analyzed.

The VR intervention will require the use of the patient's head to navigate the characters in the game (i.e. looking left, right, up or down) and will not require the patient to get out of bed, move their arms, or legs. The research assistant (or other member of the research team) will initiate the VR intervention for patient, record the duration of intervention, and denote any reports of distress including nausea or dizziness (See Appendix I). Parents will be asked to remain at the bedside with the patient throughout the VR intervention, keep the rails of the bed up at all times, push the call light to notify the RA when the child has completed the game, and advocate for their child if the VR experience is poorly tolerated as an additional safety measure.

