At the closure of the game the research assistant (or other member of the research team) will remove the headset. The headset will then be thoroughly cleaned with hydrogen peroxide wipes and/or replacement of facemask according to standard infection control recommendations for the CHARIOT VR device before the next study participant's use. See Appendix J.

After intervention and immediately preceding sedation, anxiety measures using m-YPAS will be reassessed by the medical provider (attending physician or fellow physician).

The physician will perform the sedation per CHW ED sedation policy. The sedation will be administered and as appropriate the patient discharged. Child life consultation by nursing staff or medical provider as an adjunct to patient care during ED course will be permitted per standard procedure and noted. See Appendix K.

Follow-up with the family will be performed by the research assistants (or other member of the research team) between 7-14 days after ED discharge consistent the procedures followed previously (Pearce et al., 2017). Phone, secured REDCap email/text, and mail surveys will be sent. One PHBQ and pain survey will complete the study. Follow up contact via email/text will include instructions for the parent to complete the PHBQ survey and pain questions via a link that will be provided through the secured REDCap database and record their responses electronically. Script content will be consistent with the example documented in Appendix L. The phone follow-up attempts will take place during the hours agreed upon by the parent(s)/guardian(s). The phone follow-up attempts will occur no more than two times per day during the follow-up period. During the phone, email, text or mail follow-up, the PHBQ post-sedation will be administered to assess the degree of change PONB changes post-sedation as well as 3 additional questions regarding post-discharge pain treatment: (1) Was your child prescribed an opiate medication (ie. oxycodone) prescription for pain control at home? (2) Did you fill this prescription? (3) Have you given your child an opiate medication for the pain following discharge from the ED? This phone survey was utilized in a prior study and took no longer than 5 minutes to complete. If the parent(s)/guardian(s) are not reachable by phone after the period specified above, then a paper copy of the follow-up survey will be mailed to him/her along with a self-addressed stamped envelope for return of the survey.

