**O. PROCEDURES TO BE EMPLOYED IN ANALYZING DATA AND THE ANTICIPATED SIGNIFICANCE OF THE PROPOSED STUDY.**

- Missing data handling: Every effort will be made to avoid missing data. Using logistic regression, the assumption of missing at random (MAR) will be explored. In general, we will assume MAR, and multiple imputations will be used for items.
- Patient demographic and characteristics data: To evaluate comparability between treatment groups regarding patient demographic and baseline characteristics, descriptive statistics such as mean, median, standard deviation, range, frequency will be used to summarize the data. To compare the two groups, a student's t-test will be used for continuous variables. Where necessary, for parametric assumption, we will employ appropriate transformations with justifications. If data cannot be appropriately transformed, we will compare continuous variables between the two groups using a Mann-Whitney test. A chi-square or Fisher's exact test will be used for categorical variables.
- Analyses for Specific Aim #1: A chi-square or Fisher's exact test will be used to compare the proportion of negative behavioral change between two groups. Logistic regression analysis will be performed to compare the proportions after adjusting for covariates.
- Analyses for Specific Aim #2: The change of anxiety scores will be compared between two groups using a student's t-test or a Mann-Whitney test if the parametric assumption is not met and the data cannot be appropriately transformed. A generalized linear model will be used to compare the change of anxiety scores after adjusting for covariates.
- Statistical software SAS version 9.4 will be used for the analyses and a p-value < 0.05 will be considered as statistically significant.

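### The only post-randomisation m-YPAS rating in Aim 2 is made by the child's own physician, with no masking to arm described for the rater or the scorer

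*Combined protocol and SAP*

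**What the plan says.** **Who rates.** Section D (Measures, Anxiety) gives both ratings to the treating physician: "The patient's provider (attending physician or fellow physician) will assess the patient's anxiety using the m-YPAS twice during our study". The study procedures in the same section repeat this for the second rating: "After intervention and immediately preceding sedation, anxiety measures using m-YPAS will be reassessed by the medical provider".

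**Who totals the form.** Section D adds "This will be given to the research assistant (or other member of the research team) to score" and "The score will not be shared with the physician". The procedures give the research assistant role the task of fitting the headset, starting the game and recording its duration.

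**Timing.** The baseline rating comes before allocation: "Patients will then be stratified into high and low anxiety groups based on their baseline m-YPAS score", and randomisation follows. On the headset, Section D says "The VR device will be removed when the X-ray technician team arrives to the room prior to the start of the sedation". It also plans to record the interval from removal to the m-YPAS, so removal comes before the rating. Removal is meant to fall within 5 minutes of the start of sedation.

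**Analysis.** Section O, Specific Aim #2: "The change of anxiety scores will be compared between two groups using a student's t-test or a Mann-Whitney test", with a covariate-adjusted model in addition.

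Nothing in the protocol text says whether the rater or the scorer knows the arm. Figure 1 and the appendix holding the m-YPAS form are not reproduced in the copy reviewed.

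**The concern.** The m-YPAS is a physician's assessment of the child, so it depends on judgement. The protocol's stated hypothesis is that VR lowers anxiety. A rater who knows the arm and shares that expectation may rate VR children slightly lower without intending to.

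The one concealment step works in the wrong direction. It keeps the total from the physician, but the physician has just made the ratings that produce it, and knowledge of the arm is untouched. The scorer is not described as masked either.

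What is at stake is the reading of the secondary aim. A lower mean score in the VR arm could be a calmer child, a more favourable rating, or both. Adjusting for covariates does not help, because a rating shift caused by knowing the arm coincides with the arm itself.

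**Working it through.** **Step 1: where bias can enter.** Change = second rating − baseline rating. Baseline is rated before randomisation, so arm cannot affect it. If raters score VR children lower by an average of *b* at the second rating, the expected difference in change between arms is the true effect minus *b*. The whole of *b* reaches the comparison.

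**Step 2: the plan's own figure.** Section E sizes the trial on Aim 1 (25% against 10%, 80% power, significance level 0.05, taken here as two-sided). The unpooled normal formula gives

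n = (1.96 + 0.8416)² × (0.25×0.75 + 0.10×0.90) / 0.15² = 7.849 × 0.2775 / 0.0225 = 96.8, so 97 per group.

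Allowing for 20% loss: 2 × 97 / 0.8 = 242.5, so 243. Both stated numbers reproduce. Section E gives no size or power figure for Aim 2.

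**Step 3: illustration for Aim 2.** Assumptions: no true VR effect, two-sided 5% test, normal approximation, and a rating shift *b* in units of the SD of the change score. The documents supply neither *b* nor the SD.

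SE = √(2/n). For n = 97, SE = 0.1436 SD.

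Rejection rate = 1 − Φ(1.96 − b/SE) + Φ(−1.96 − b/SE).

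For b = 0.2: b/SE = 1.393, and the rate is 1 − Φ(0.567) + Φ(−3.353) = 0.286.

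| Shift (SD) | 97 per arm | 121 per arm |
|---|---|---|
| 0 | 5% | 5% |
| 0.1 | 11% | 12% |
| 0.2 | 29% | 34% |
| 0.3 | 55% | 65% |
| 0.4 | 80% | 88% |

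The second column of rates is shown because the m-YPAS is completed in the ED before any loss to follow-up, so close to 243/2 = 121.5 per arm could be scored. A larger sample makes the problem worse, because bias does not shrink with n.

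**Step 4: scale.** The true difference detectable with 80% power at 97 per arm is (1.96 + 0.8416) × 0.1436 = 0.40 SD. A shift of 0.2 SD is half of that.

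**The case against.** **The magnitude is hypothetical.** This stands. The table follows from chosen inputs and says nothing about how large rater bias would be in this trial. It shows only how sensitive the Aim 2 test is to a modest shift.

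**The physician may not know the arm.** A reader might infer that the physician watches the VR session. The documents do not say where the physician is during VR, or that the allocation is disclosed. What they support is narrower: nothing is described that would keep the rater unaware.

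**The second rating is not the whole outcome.** A reader might infer that it is. Section O analyses change, and the baseline half cannot be biased by arm. The second rating is the only post-randomisation half, which is enough for the point.

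**Masking may not be free.** Because the headset is already off, a reader might infer that masking needs no extra staff. The documents do not establish this. They do not show that two physicians are available for each child, and the time between headset removal and sedation is short. Child and parent know the arm. Section H has medical providers evaluate nausea or dizziness at the bedside, and Section D asks parents to speak up if VR is poorly tolerated. Masking will therefore sometimes fail, and any request for discretion must give way to these provisions.

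**Some remedies would add bias.** This also stands. Bringing in a different rater only for VR children would put rater differences into the change score by arm. Closing a curtain only for VR children would reveal the arm. Restricting the analysis to masked ratings selects on something that happens after randomisation: a VR child who feels unwell is more likely to unmask the physician, so dropping such children could favour VR.

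**Conclusion.** The point holds for the secondary aim. As written, the only post-randomisation component of the Aim 2 outcome is rated by the child's own physician and totalled by a role that runs the intervention, with no masking described for either. Any arm-related shift passes in full into the change score, and the planned analysis cannot remove it.

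Its size cannot be estimated from the documents. Under the stated assumptions, a shift of 0.2 SD gives about 29% false positives at 97 per arm (34% at 121) instead of 5%.

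A reader might infer that the trial's main conclusion is compromised. It is not on this ground: the primary outcome is the parent-reported PHBQ, and 97 per group and 243 in total stand. This is a worthwhile, low-cost improvement to a secondary aim. Whether the rater knew the arm cannot be reliably recovered after enrolment.

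**What to change.** In Section D (Measures, and the study procedures):

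- State that the m-YPAS rater is not told the allocation.
- In both arms alike, keep the door or curtain closed during the wait before sedation, have any headset out of sight before the rater enters, and ask families not to volunteer the arm. State that symptoms and safety concerns are always reported and that the bedside evaluation in Section H takes priority.
- Use the same rater for both ratings where possible, and do not change rater in the VR arm only.
- Have the form totalled by study ID, without arm information.
- Add a tick-box recording whether the rater knew the arm (yes/no).

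In Section O (Specific Aim #2):

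- Keep all randomised children in the main analysis.
- Report the tick-box frequency by arm. Treat any analysis by rater awareness as descriptive only.
- Where masking fails, state the limitation when reporting Aim 2.

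Cost: protocol wording, one form item and a small procedural burden. The design calls for no additional assessor and no change to the sample size. Masking will be imperfect in a busy ED with at most about 5 minutes between headset removal and sedation, and the tick-box will show how often it failed.

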#### **D. DESIGN AND METHODS**

[figure not shown]
- Study Design: This is a randomized control trial.
- Site: Children's Hospital of Wisconsin (CHW) ED.
- Subjects: Subjects will be recruited during ED hours when research assistants (or other member of the research team) are available.
  - Inclusion criteria: Children ages 6 years to 17.5 years old receiving procedural sedation with IV ketamine in the CHW ED for long bone fracture reduction. See Appendix A. This age group is most likely to achieve positive effects, fit the VR headset equipment, and tolerate the device without adverse side effects.
  - Exclusion criteria: Patients with moderate to severe developmental delay will be excluded because the anxiety scoring tools have not been validated in this population. Non-English-speaking patients/families will be excluded because the parent survey questionnaire has not been developed and validated in languages other than English. Patients taking psychotropic medications will be excluded because these pharmaceuticals may affect measuring the primary outcome, PONB changes. See Appendix B. Patients with a history of severe motion sickness will be excluded. Patients currently experiencing nausea will be excluded. Patients who have severe visual impairment will be excluded as the VR intervention engages patients in an interactive game that requires navigation through visual content on the VR headset/screen. Patients with an expected admission to the hospital post-procedure will be excluded because outcome data may be affected by this. For a portion of patients this will not be known until after the fact. These patients will be excluded and considered screening failures.

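### A printed, fixed block size of 4 in two anxiety strata, with visible allocation and no described concealment or score lock, leaves upcoming assignments more predictable than they need to be

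*Combined protocol and SAP*

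**What the plan says.** All of this is in section D (Design and Methods) unless noted.

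- **Allocation.** Children are split into two strata "based on their baseline m-YPAS score (score of 40 or greater being highly anxious") and then "randomized in blocks of 4 by a computer to either the control or experimental group on a 1:1 ratio". No other block size is mentioned.
- **Setting.** There is one centre: "Site: Children's Hospital of Wisconsin (CHW) ED". Recruitment takes place when research staff are available.
- **Rating the scale.** The baseline m-YPAS "will be completed at baseline by the patient's medical provider (attending physician or fellow physician").
- **Scoring the scale.** The completed form passes to the research team: "This will be given to the research assistant (or other member of the research team) to score". The rater is kept unaware of the result: "The score will not be shared with the physician".
- **Delivery.** The research assistant, or another team member, also identifies patients and reviews eligibility. For children in the VR arm the same role "will initiate the VR intervention for patient, record the duration of intervention".
- **Visibility.** The control arm has ordinary distraction but no VR and no sham.
- **Order of steps.** Consent comes first, then the baseline m-YPAS and questionnaire, then stratification and randomisation.

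The plan does not say how the computer releases an assignment, who can see earlier assignments, or whether the score is fixed before the arm appears. Blinding is not described.

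**The concern.** In a block of 4 with two children per arm, the last assignment always follows from the first three, and sometimes the last two follow from the first two. With only two running blocks in one department and every past assignment visible at the bedside, a small team could keep track. Someone who can foresee the next arm could influence which families are approached, drop a child after scoring, or mis-total a form near the cut-off so that the child draws from the other stratum.

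The primary outcome is reported by parents who know the arm, so comparability of the groups at entry is one of the main protections the primary comparison has. Selection acting through predicted assignments would weaken it. The covariate-adjusted logistic regression in section O names no covariates and could not correct for unmeasured selection.

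**Working it through.** **The plan's own figure.** The documents give no predictability figure. The only stated number used here is the sample size in section E: 25% versus 10%, 80% power, alpha 0.05 (two-sided assumed), 20% dropout. With unpooled variance, n per arm = (0.25×0.75 + 0.10×0.90) × (1.960 + 0.842)² / 0.15² = 96.8, so 97. Then 194/0.80 = 242.5, so 243. This reproduces, and nothing below changes it.

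**Inputs.** Block size 4, ratio 1:1, two strata, one site (section D); N = 243 (section E).

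**Step 1: the child's stratum is known and its history has been tracked.** There are six possible orders of two VR and two control. Taking the four positions in turn:

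| Position in block | Chance the assignment is certain | Chance a best guess is right |
|---|---|---|
| 1 | 0 | 1/2 |
| 2 | 0 | 2/3 |
| 3 | 1/3 | 1/3×1 + 2/3×1/2 = 2/3 |
| 4 | 1 | 1 |

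Certain share = (0 + 0 + 1/3 + 1)/4 = 1/3, and 243/3 = 81 children. Best-guess accuracy = (1/2 + 2/3 + 2/3 + 1)/4 = 17/24 = 70.8%. Simulating two strata with N = 243 gives 33.0% certain, slightly lower because final blocks may be incomplete.

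**Step 2: approach and consent, with the stratum not yet scored.** In the long run each stratum's next assignment is certainly VR with probability 1/6 and certainly control with probability 1/6. The arm is then certain only if both strata point the same way: 2 × (1/6)² = 1/18 = 5.6% (simulated 5.4 to 5.5%). Best-guess accuracy depends on the share of highly anxious children, which the documents do not give. For an assumed share of 30 to 70%, simulation gives 66 to 67%; for a share of 20% it is 68%. Staff who can judge a child's anxiety by eye move back towards the Step 1 figures.

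**Step 3: at scoring.** At least one stratum has a certain next assignment with probability 1 − (2/3)² = 5/9, about 55% in simulation. The two strata are certain and opposite, so that the total alone would decide the arm, with probability 2 × (1/6)² = 1/18, about 5.5%.

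**Step 4: effect of varying the block size.** The simulated observer knows the menu of sizes but not which size is running.

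| Scheme | Certain | Best guess right |
|---|---|---|
| Fixed 4 | 33.3% | 70.8% |
| Random 4 and 6 | about 5% | about 69% |
| Random 4, 6 and 8 | about 2% | about 68% |

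**Step 5: possible bias.** Suppose children enrolled when VR is predicted have an underlying risk lower by δ than those enrolled when control is predicted, and staff act on every prediction. With best-guess accuracy p, the bias is δ × (2p − 1). The documents give no δ; 5 to 10 points is an assumption.

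- Fixed 4: 2 × 0.708 − 1 = 0.417, so 2.1 to 4.2 points.
- Random 4, 6 and 8: 2 × 0.679 − 1 = 0.358, so 1.8 to 3.6 points.
- Fixed 4 with the stratum unknown, p = 0.66 to 0.67: 0.32 to 0.34, so 1.6 to 3.4 points.

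The target effect is 15 points. Since 0.358/0.417 = 0.86, varied blocks alone leave about 86% of the modelled bias.

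**The case against.** Fixed small blocks within strata are a common choice, the assignment is made by computer after consent, and nothing here is an arithmetic error or contradiction. A reader might also draw four stronger conclusions, which the documents do not support.

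- *That a third of assignments are known when families are approached.* Consent comes before the m-YPAS rating and stratification. At approach the certain share is about 5%; one third applies only once the stratum is known.
- *That the staff who deliver VR decide the anxiety rating.* A physician makes the rating and is not told the score. The team only totals it. Moving a child across 40 would mean mis-totalling a completed form, which is a narrower route than judging a borderline child.
- *That one person does everything.* The protocol names a role, the assistant or another team member, and does not say who sees the allocation history. Equally, it describes no separation of duties, so none can be credited.
- *That comparability has been broken.* The text shows an opportunity, not an event. The bias figures rest on an assumed risk difference and on staff acting on every prediction, so they are a scenario rather than an expected size.

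It is also fair to object that varying the block size, taken alone, does little to guessing. That stands, and it determines the order of the remedy. What remains of the point is that guessing before the stratum is known is still well above 50%, and that no safeguard is described at the step where the score fixes the stratum.

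**Conclusion.** The point holds as an inexpensive improvement to the plan, not as a flaw that invalidates it. One third of allocations (about 81 of 243) are certain and 70.8% are guessable for staff who know the block size, have followed the stratum and know which stratum the child is in. Before scoring, the figures are about 5% and about 66 to 67%, the latter for an assumed high-anxiety share of 30 to 70%. At the cut-off of 40 the exposure is limited to totalling the form or losing a child after scoring. Open allocation is inferred from the absence of a sham, not stated. If the assumed 5 to 10 point risk difference applied, the bias could reach 2.1 to 4.2 points against a 15-point target; nothing in the documents shows that it would.

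**What to change.** 1. State in section D that the baseline m-YPAS total and stratum are entered and locked in REDCap before the arm is released. State also that the block scheme and upcoming sequence are withheld from anyone who recruits, scores or treats.
2. Replace the fixed block size with randomly varying blocks, for example 4, 6 and 8, within each stratum. Keep the sizes out of the protocol text that site staff see.

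The two belong together: the second removes most of the certainty but little of the guessing, so the first is needed with it.

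The cost is a regenerated list, a short amendment and the set-up of the lock. The largest possible imbalance within a stratum rises from 2 (half of a block of 4) to 4 (half of a block of 8). N stays at 243.
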